3.1. Study Objectives

Primary Objectives

1. To describe the demographic and clinical characteristics of patients who have received palbociclib combination treatments in line with locally approved indications.
2. To summarize adjuvant therapies received for the treatment of early or locally advanced breast cancer (Stages 0-IIIa).
3. To describe treatments received in the advanced/metastatic setting, before and after palbociclib combination use.
4. To describe dosing and dose changes, interruptions, delays, and discontinuations associated with palbociclib use in clinical practice.
5. To describe supportive therapies received by patients while receiving palbociclib combination treatments.
6. To determine clinical outcomes including:
 - Proportion of patients who are progression free at quarterly intervals (eg, 3, 6, 12, 18 months);
 - CCI [REDACTED]

- Objective response rate (ORR);
- Clinical benefit rate (CBR) – if feasible;
- Proportion of patients alive 1 and 2 year post palbociclib combination initiation (depending on availability of follow-up data);
- Best response (complete response, partial response, stable disease, disease progression);
- Time to death.

CCI

4. ANALYSIS SETS/POPULATIONS

4.1. Full Analysis Set

Only patients who meet the completed inclusion and exclusion criteria described in Section 3.0 and for whom a core medical record review was conducted will be included in the full analysis set (FAS).

4.2. Interim Analysis Set

Only patients who meet the completed inclusion and exclusion criteria described in section 3.0 and for whom an interim medical record review was conducted (Germany only) were included in the interim analysis set (IAS). The interim analysis did not derive the clinical outcomes variables outlined in Section 5.5 (including CCI, progression free survival and clinical benefit rate).

4.3. Stratifications and Subgroups

Stratifications will be conducted to assess differences in outcomes by line of therapy, demographics, treatments clinical characteristics or ‘responders’ and ‘non-responders’ to treatment, however these will be only descriptive in nature. Responders and non-responders will be defined according to the best recorded response to palbociclib treatment.

For wave 1 countries already conducted (US, Argentina and Germany (interim)) additional stratifications included:

- Disease stage at initial diagnosis (ABC vs mBC);
- Combination partner (AI/letrozole vs fulvestrant);
- Treatment sequence (line of therapy: AI 1st line, fulvestrant 1st – 3rd line);

- Age (up to 65, greater than 65 years);
- Metastases, visceral vs. non-visceral disease.

Additional ad hoc stratifications were completed for the US 2017 analysis, as below:

- Age classification by indication (up to 65, >65);
- ECOG at palbociclib initiation for all patients and by indication;
- Palbociclib starting dose 125 mg vs not 125 mg for all patients and by indication;
- Disease progression with initial control vs without initial control;
- Visceral status (mBC only) by indication;
- Alternative classification of metastases by indication (bone metastases only, visceral disease only, bone and visceral, neither (other)).

For analysis of the wave 2 countries (Germany (core), Canada, UK, Italy, France, Belgium, Switzerland, Japan, Spain, Netherlands and Portugal), the following stratifications are requested (dependent of sample size):

- Combination partner (AI/letrozole vs fulvestrant);
- Treatment sequence (line of therapy: AI 1st line, fulvestrant 1st – 3rd line);
- Age <50, ≥50 years old;
- Age <65, ≥65 years old;
- Age <75, ≥75 years old;
- Starting dose 125 mg vs. non 125 mg.

For clinical outcomes variables only:

- Prior chemotherapy by palbociclib indication (AI/letrozole vs fulvestrant);
- Menopause status (peri- or post- menopausal);
- Disease stage at initial diagnosis (ABC vs mBC).

For treatment patterns variables only, the following stratifications may include:

- Academic vs. community institution.

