In October 2016, palbociclib was granted approval to be used in combination with fulvestrant. This was following the success of the phase III PALOMA-3 trial, conducted in patients with advanced/metastatic HR+/HER- breast cancer that had relapsed or progressed during endocrine therapy. The PALOMA-3 trial demonstrated a median progression-free survival of 9.2 months in those receiving fulvestrant in combination with palbociclib vs. 3.8 months in patients receiving fulvestrant with placebo.⁸ Palbociclib was approved by the EMA in November 2016 to be used in combination with an aromatase inhibitor or with fulvestrant in patients who had previously received endocrine therapy.⁹

As a result of the recent approval of palbociclib, there is scarce information regarding how and when palbociclib combination is prescribed in routine clinical practice, palbociclib treatment patterns, the outcomes associated with palbociclib use and the characteristics of palbociclib responders. Therefore, real world data on the characteristics, treatment patterns and clinical outcomes among patients receiving palbociclib combinations to treat HR+/HER-ABC/MBC will provide valuable insight to help inform treatment decisions.

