- Agrees to participate in the study and complete the CRFs.

¹ Breast surgeons/general surgeons/gastro-surgeons may also be included as relevant treaters in Japan.

Patient inclusion criteria

- ≥ 18 years old;
- HR+/HER- breast cancer diagnosis with confirmed metastatic or advanced disease;
- Received palbociclib plus letrozole/aromatase inhibitor or palbociclib plus fulvestrant in line with the licenced indication(s);
- No prior or current enrolment in an interventional clinical trial for ABC/MBC;
- Minimum of three months of follow up data since palbociclib with fulvestrant initiation, or minimum of six months of follow up data since palbociclib with letrozole/aromatase inhibitor initiation (core medical record review);
- Minimum of three months of follow up data since palbociclib initiation (German interim medical record review only);
- Inoperable or recurrent breast cancer (Japan only).

In order to ensure that sufficient data is captured for each indication, indication soft quotas will be enforced. This will be determined on a country by country basis.

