- Line of therapy that palbociclib is received (T);
- Treatments received in the line of therapy prior to palbociclib (T-1);
- Treatments received in the line of therapy post palbociclib (T+1).

Palbociclib dosing characteristics**To be abstracted directly from the medical records:**

- Palbociclib starting dose;
- Reasons for starting at a dose lower than 125 mg/day;
- Number of palbociclib dose changes;
- Details of each dose change (eg, dose increase, dose decrease, dose interruption, cycle delay);
- Date of dose change;
- Reason for dose change (eg, side effects/toxicity, lack of response);
- Status of combination partner therapy at dose change (eg, if continued or stopped).

To be derived

- Time from palbociclib initiation to first dose change;
- Duration of dose interruption;
- Duration of cycle delays.

Supportive therapies received during palbociclib treatment**To be abstracted directly from the medical records:**

- Supportive therapies received during palbociclib treatment.

Clinical Outcomes**To be abstracted directly from the medical records:**

- Initial response recorded;
- Time from palbociclib initiation to initial response;
- Frequency with which response to palbociclib was assessed;
- Proportion with complete response;
- Proportion with complete response defined by radiological evidence;
- Proportion with partial response defined by radiological evidence;
- Time from palbociclib initiation to complete response;
- Proportion with partial response;
- Time from palbociclib initiation to partial response.

To be derived

- Objective response rate defined as the proportion of patients achieving complete or partial response on palbociclib;
- Clinical benefit rate defined as the proportion of patients achieving complete or partial response, or stable disease ≥ 24 weeks on palbociclib. Stable disease will be defined as no evidence of complete or partial response, and no progression on palbociclib therapy for 24 weeks or greater;
- Proportion with stable disease ≥ 24 weeks on palbociclib;

█ [REDACTED]

- Progression free survival (if applicable) defined as the time from the start of palbociclib to the first subsequent progression or death;
- Time to death, defined as the time from the start of palbociclib to death;

█ [REDACTED]

- Progression free at 3, 6, 12, 18, 24 months defined as the proportion of patients who have no documented progression at defined time points;

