7.2. Statistical Methods

Based on the descriptive nature of the study, all study measures will be summarized descriptively through the tabular and graphical display of mean values, standard deviations, and ranges for continuous/numeric variables of interest. For categorical variables, frequency distributions (n, %) will be displayed. Missing and unknown categories for each variable also will be presented. Percentages will be calculated excluding missing values. All endpoints will be calculated for the overall population and by the stratification variables listed in [Section 4.3](#) (sample sizes permitting).

To show how one treatment line moves to the next, adjacent treatment combinations will be cross-tabulated (showing frequencies), eg, treatments received in the line prior to palbociclib (T-1) will be cross-tabulated with treatment line at which palbociclib was received (T), T will be crossed by treatments received at the line following palbociclib (T+1) and T+1 will be crossed by treatments received at the second line following palbociclib (T+2.)

For each of the 4 lines, whether or not that line is still ongoing or not will be described (this excludes T-1 as that line cannot be ongoing). For those not still ongoing (ie, the line has ended), the reason for ending will be described.

Time-to-event outcomes (ie, time to treatment start, time to dose reduction, treatment duration, CCI, PFS, death) will be described using the Kaplan-Meier method. In addition to reporting median event times for these measures, time-dependent event rates (eg, proportion of patients without event at various time points from a starting point of interest) will also be reported based on lifetables derived from the Kaplan-Meier analyses. All analyses will be conducted using Stata (version 14.2 or higher) statistical software and IBM SPSS Survey Reporter.

The outlined statistical methods anticipate that the selected sample is randomly drawn from normally distributed populations. However, this study will employ a convenience sample; thus, results may not be generalizable to the entire universe of patients receiving palbociclib.

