7.2.1. Definitions of Clinical Outcomes

Objective Response Rate (ORR)

Objective response rate defined as the proportion of patients achieving complete or partial response on palbociclib combination therapy.

Clinical Benefit Rate (CBR)

Clinical benefit rate is defined as the proportion of patients achieving complete or partial response, or stable disease ≥ 24 weeks on palbociclib combination therapy. Stable disease will be defined as no evidence of complete or partial response, and no progression on palbociclib therapy for 24 weeks or greater.

CCI [Redacted]

[Redacted]

Progression Free Survival (PFS)

Progression Free Survival is defined as the time from palbociclib combination treatment initiation until the earliest of (1) clinician-documented progression while on palbociclib (2) death, (3) start of a new therapy line after final palbociclib dose if the reason for discontinuation of palbociclib was disease progression, or (4) last available follow-up. Patients who did not experience a progression event (items 1, 2 and 3) will be censored at date of last available follow-up. PFS (in months) will be calculated as (first event date - palbociclib initiation date + 1)/30.4.

PFS will be analysed using a Kaplan-Meier (KM) survivor function. A table will show the survivor rate at 3 month intervals and will also show the 3 month incremental survivor rate, ie, the survivor rate from the start of that 3 month interval rather than from time zero. The median survival (if the median is reached) and a KM chart will also be shown. Time zero will be taken at the point of palbociclib initiation.

CCI [Redacted]

[Redacted]

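### Responder strata based on best response ever recorded would bias PFS and survival counted from palbociclib start in favour of responders

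*SAP*

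**What the plan says.** The opening paragraph of SAP 4.3 states the purpose: "Stratifications will be conducted to assess differences in outcomes by line of therapy", and the same sentence goes on to name responders and non-responders. The grouping rule follows: "Responders and non-responders will be defined according to the best recorded response to palbociclib treatment". Protocol 8.7 (Subgroup Analysis) has the same rule and calls the stratifications exploratory and descriptive.

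SAP 7.2 sets the scope: "All endpoints will be calculated for the overall population and by the stratification variables listed in" Section 4.3, sample sizes permitting. Protocol Table 1 likewise lists PFS, progression-free proportions and 1- and 2-year survival as outcomes for all patients and for subgroups.

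The clock starts at treatment start. For PFS, SAP 7.2.1 says: "Time zero will be taken at the point of palbociclib initiation". For survival, SAP 5.5 (Clinical Outcomes) says: "Time to death, defined as the time from the start of palbociclib to death". Both are to be described by Kaplan-Meier.

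Two passages point towards a narrower use. Responder status is in none of the bulleted lists of SAP 4.3, including the one headed "For clinical outcomes variables only". SAP 2 names as knowledge gaps "the outcomes associated with palbociclib use and the characteristics of palbociclib responders", which suggests an interest in describing who responds.

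**The concern.** Best recorded response is known only after treatment has run for some time. A patient joins the responder group only by surviving, not progressing and staying under observation until a response is recorded. Responders therefore cannot have an event before their response date, whereas all patients who progress or die before responding are counted as non-responders. A Kaplan-Meier curve from palbociclib start credits responders with that event-free waiting time.

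If medians, progression-free rates or survival rates are displayed by this stratum, part or all of the gap is an artefact. Calling the display descriptive means that no hypothesis test and no primary estimate depends on it, but the displayed medians and rates are still not a valid contrast. Both documents say that the results should help inform treatment decisions, and Protocol 11 foresees publication. Protocol 8.9 discusses selection and channeling bias but not this one.

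**Working it through.** The documents give no figure for outcomes by response, so there is nothing to reproduce. The check asks how large a gap appears when response is irrelevant by construction.

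**Inputs from the documents.** Median PFS is 24.8 months with letrozole (Protocol 6, SAP 2) and 10.8 months with fulvestrant (Protocol 6; SAP 2 prints 9.2). Minimum follow-up is 6 months for letrozole/AI and 3 months for fulvestrant (SAP 3). Time zero is palbociclib start.

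**Assumptions not in the documents.** PFS is exponential, S(t) = 0.5^(t/median). A share p of patients could respond, and response time is independent of PFS. Responder means a response recorded before progression or censoring.

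**Hand check.** Let p = 0.5 and let every potential response occur at month r, set equal to the minimum follow-up so that nobody is censored earlier. For t > r:

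- Responders: S(t) / S(r)
- Non-responders: (1 − p) S(t) / [1 − p S(r)]

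Letrozole/AI, r = 6: S(6) = 0.5^(6/24.8) = 0.846 and S(12) = 0.715. At 12 months responders show 0.715/0.846 = 84.6% and non-responders 0.5 × 0.715/(1 − 0.423) = 61.9%. The truth is 71.5% in both groups.

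Fulvestrant, r = 3: S(3) = 0.5^(3/10.8) = 0.825 and S(12) = 0.463. At 12 months responders show 0.463/0.825 = 56.1% and non-responders 0.5 × 0.463/(1 − 0.412) = 39.4%. The truth is 46.3% in both groups.

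**Simulation.** There were 300,000 patients in each of 12 scenarios per indication: p = 0.3, 0.5 or 0.7, with response time uniform from month 2 to month 3, 6, 9 or 12. Censoring was uniform from the minimum follow-up to 36 months. Ranges over the 12 scenarios:

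| True median PFS | Apparent median, responders | Apparent median, non-responders | Gap (months) | 12-month progression-free, responders vs non-responders | True 12-month value |
|---|---|---|---|---|---|
| 24.8 | 27.2–31.7 | 14.3–23.7 | 3.5–17.4 | 77–86% vs 53–69% | 71.5% |
| 10.8 | 13.3–17.4 | 5.0–9.8 | 3.5–11.3 | 54–71% vs 28–44% | 46.3% |

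The middle scenario (p = 0.5, months 2 to 9) gives 30.2 vs 20.4 months and 16.1 vs 7.4 months.

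**Different response-time model.** With exponential time to response (median 3 or 6 months), half of patients able to respond and censoring up to 30 months, the null hazard ratio for PFS is 0.53–0.63 (median 24.8), 0.52–0.60 (10.8) and 0.53–0.60 (9.2). It should be 1.

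**Survival.** Death was set at PFS time plus an exponential post-progression time with a median of 9 to 24 months (assumed). The false gap at 12 months is 2–17 percentage points in the 24.8 case and 4–25 in the 10.8 case. At 24 months it is 4–24 and 4–28 points.

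**Landmark on the same null data.** Grouping by response up to the landmark, among patients still event-free and in follow-up, gives event-rate ratios of 0.99–1.01 (letrozole/AI, 6 months) and 0.97–1.02 (fulvestrant, 3 months). The artefact disappears.

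**The case against.** The strongest reply is that the plan does not clearly call for this display. SAP 7.2 refers to variables listed in Section 4.3, and responder status is in none of the lists there. For wave 2, the list of requested stratifications and the separate list for clinical outcomes both omit it. The US ad hoc list does contain a response-type split (progression with or without initial control), so the sponsor lists such a stratum when it wants one. Describing baseline features by response would be harmless, and the table shells, which might settle the matter, are not in the text available.

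This has weight and is why the point is conditional. It does not remove the problem. The general sentence of SAP 4.3 speaks of differences in outcomes and names responders. The wave 1 and US lists are described as additional to it, and the wave 2 list does not withdraw it. Nothing excludes time-to-event endpoints.

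Three smaller objections stand in part:

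- The size of the gap rests mostly on assumptions, and a pure null cannot show what share of a real gap would be artefact.
- The survival runs count deaths before the minimum follow-up. SAP 3 requires, for example, "Minimum of three months of follow up data since palbociclib with fulvestrant initiation". If that makes early deaths ineligible, the false 12-month survival gap shrinks to 1–11 points (24.8 case) and 3–22 points (10.8 case), in the same direction.
- Complete or partial response is the natural reading of responder, given the ORR definition. The missing definition is therefore a matter of detail.

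**Conclusion.** The concern holds. SAP 4.3 and 7.2 read together extend the responder stratum to PFS and survival measured from palbociclib start, and that contrast is biased in favour of responders. With response irrelevant by construction, the false gap in median PFS is 3.5–17.4 months when the true median is 24.8 and 3.5–11.3 months when it is 10.8. These sizes rest on assumed responder shares, response timing, exponential PFS and follow-up to 36 months. The direction was the same in every scenario. No primary overall-population estimate and no test is affected. The plan should nevertheless be changed, because the rule applied literally produces a misleading display and the correction is simple.

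**What to change.** Amend SAP 4.3 and 7.2 and Protocol 8.7 as follows.

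1. Name the best-response categories that make a responder.
2. State that the responder stratification applies only to baseline characteristics and treatment history.
3. If PFS or survival by response is wanted, treat response as a time-dependent status, or prespecify a landmark for each indication that fits the minimum follow-up (for example 3 months for fulvestrant and 6 months for letrozole/AI). Fix response status at the landmark, include only patients alive, progression-free and in follow-up then, and start the clock there.
4. If responder means complete or partial response, do not tabulate ORR or CBR by responder status, because the responder cells would be fixed by definition.

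Items 1, 2 and 4 cost only wording. Item 3 costs one extra Kaplan-Meier run for a landmark, with these downsides:

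- About 15% of letrozole/AI patients (1 − 0.846) and 17–18% of fulvestrant patients (1 − 0.825) leave that one display. A 6-month landmark for fulvestrant would lose 1 − 0.5^(6/10.8) = 32% to events, and about 38% with censoring.
- Late responders count as non-responders. In the simulation the landmark captures 43–95% of eventual responders for letrozole/AI and 14–97% for fulvestrant. A time-dependent status avoids this loss.
- Both methods need response dates. SAP 5.5 plans to abstract time to response, but SAP Appendix 1, Table 6 still shows the CRF source for complete and partial response and their timing as to be confirmed. That must be settled first.

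### The wave 2 starting-dose stratification pools AI and fulvestrant patients, so outcome differences by starting dose may partly reflect the mix of combination partners

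*SAP*

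**What the plan says.** SAP 4.3 introduces the wave 2 list with "the following stratifications are requested (dependent of sample size" and includes "Starting dose 125 mg vs. non 125 mg" with no reference to indication. The same list has "Combination partner (AI/letrozole vs fulvestrant" and "Treatment sequence (line of therapy: AI 1st line, fulvestrant 1st – 3rd line" as separate items, neither crossed with starting dose. The only wave 2 item crossed with indication is in the clinical-outcomes list: "Prior chemotherapy by palbociclib indication (AI/letrozole vs fulvestrant".

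SAP 7.2 states how the list is used: "All endpoints will be calculated for the overall population and by the stratification variables listed in" section 4.3, where sample sizes permit. It describes no cross-classification and no adjustment. Starting dose is in the general wave 2 list, so it applies to PFS, response and survival.

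For the US, SAP 4.3 reports "Additional ad hoc stratifications were completed for the US 2017 analysis, as below", and one of those items is "Palbociclib starting dose 125 mg vs not 125 mg for all patients and by indication". Five of the six items in that US list carry a split by indication.

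**The concern.** SAP 4.3 says the stratifications serve to look at differences in outcome. The physician chose the starting dose, and SAP 5.5 collects reasons for starting below 125 mg/day, so the two dose groups are selected rather than comparable. Prognosis differs sharply by combination partner on the documents' own background figures. If the share of AI patients differs between the dose groups, a pooled table of PFS or survival by starting dose will show a difference even when dose makes none within either partner.

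Response proportions have a further route to the same problem. Minimum follow-up is six months for AI patients and three for fulvestrant patients (Protocol 8.2.1, SAP 3), so observation time also varies with partner.

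Outcome by starting dose is a result that readers may take as evidence about dose. Without the by-indication half of the display, they cannot separate dose from partner.

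**Working it through.** **Size of wave 2.** The eCRF counts in Protocol Table 2, without the German interim review, are 652 + 162 + 259 + 250 + 250 + 251 + 240 + 150 + 250 + 100 + 150 + 60 + 100 = 2874. This reproduces the core total in SAP 2.1.1. Removing the wave 1 core countries (US 652, Argentina 162) leaves 2874 − 652 − 162 = 2060 wave 2 patients.

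**Inputs from the documents.** Background median PFS with palbociclib is 24.8 months with letrozole (Protocol 6, SAP 2). With fulvestrant it is 10.8 months in Protocol 6 and 9.2 months in SAP 2. The two documents differ, so both values are run.

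**Assumptions.** PFS is exponential within each partner, and starting dose has no effect within either partner. AI shares and starting-dose shares are assumed throughout, because the documents give neither.

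**12-month PFS by partner,** S(12) = 0.5^(12/median):
- AI: 0.5^(12/24.8) = 71.5%
- Fulvestrant, 10.8 months: 0.5^(12/10.8) = 46.3%, a gap of 25.2 points
- Fulvestrant, 9.2 months: 0.5^(12/9.2) = 40.5%, a gap of 31.0 points

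**Pooled difference between dose groups.** If p1 and p2 are the AI shares in the 125 mg and non-125 mg groups, the pooled 12-month difference is (p1 − p2) × (S_AI − S_fulv). With p1 − p2 = 0.20 it is 0.20 × 25.2 = 5.0 points, or 0.20 × 31.0 = 6.2 points.

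**From dose shares to partner shares.** Suppose AI patients are 60% overall, and 10% of AI and 20% of fulvestrant patients start at a dose other than 125 mg.
- AI share in the 125 mg group: 0.54/(0.54 + 0.32) = 62.8%
- AI share in the non-125 mg group: 0.06/(0.06 + 0.08) = 42.9%
- Difference: 19.9 points of AI share, giving 5.0 or 6.2 points of 12-month PFS

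Reverse the dose shares (20% of AI, 10% of fulvestrant) and the AI shares become 0.48/0.84 = 57.1% and 0.12/0.16 = 75.0%. The difference is then −4.5 or −5.5 points.

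**Range.** The table covers AI shares of 50%, 60% and 70% and both fulvestrant medians. The last column is 125 mg minus non-125 mg, 12-month PFS.

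| Non-125 mg among AI | Non-125 mg among fulvestrant | Difference (points) |
|---|---|---|
| 15% | 15% | 0 |
| 10% | 15% | +2.6 to +3.5 |
| 10% | 20% | +4.7 to +6.2 |
| 10% | 30% | +7.9 to +10.1 |
| 20% | 10% | −3.8 to −6.1 |

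Under the same assumptions, the by-indication display shows a difference of zero in every row.

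**The case against.** The strongest reply is that the plan is descriptive and already cautious. There are no hypotheses or tests (Protocol 8.5), the stratifications depend on sample size, and Protocol 8.9 warns that treatments may be affected by channeling. Partner and line are separate stratifiers. If SAP 7.2 is read broadly, starting dose is itself tabulated by partner and by line, so an imbalance would be visible. Most of this stands, and it limits the weight of the point. It does not remove it: a descriptive table of mixed populations can still mislead, a caution is not an analysis, and seeing an imbalance does not give outcome by dose within partner.

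A second reply is that starting dose is not special. The US list also split age by indication, and the three wave 2 age cuts have no such split. That is fair, and the same addition could be made there. Starting dose has the stronger claim because it is a treatment choice that readers may interpret causally.

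A third reply is that splitting by indication leaves fulvestrant first to third line together and does nothing about frailty. This stands in full.

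Three stronger readings are tempting, and the documents do not support them:
- A reader might infer that the pooled contrast is certain to be distorted, in favour of 125 mg. That needs starting dose to be distributed differently across partners, and no such distribution is given. Zero and reversal are both possible.
- A reader might infer that wave 2 cannot be compared with the US. The US item also covered all patients, so the pooled results line up. Only the by-indication half has no wave 2 counterpart.
- A reader might infer that a planned split was withdrawn. The US split was ad hoc, and the planned wave 1 list has no starting-dose item.

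**Conclusion.** The point holds as a gap in the display. The wave 2 starting-dose stratification reaches PFS, response and survival without a split by indication, and no cross-classification or adjustment is planned. The pooled contrast is therefore open to confounding by combination partner.

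A 20-point imbalance in AI share would be worth about 5 to 6 points of 12-month PFS with no dose effect at all. That figure rests on exponential PFS, on background trial medians standing in for this cohort, and on an assumed imbalance. The documents establish that the distortion is possible and that the prognostic gap behind it is large (25 to 31 points at 12 months). They do not establish its size or sign in these data.

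**What to change.** In SAP 4.3, extend the wave 2 line "Starting dose 125 mg vs. non 125 mg" so that it is shown pooled and separately for AI/letrozole and fulvestrant patients, sample size permitting. This matches what the US item covered. For PFS, response and survival, present the by-indication results first and keep the pooled display beside them. Add one table of starting dose by partner and line so that any imbalance can be seen. State in the report that line within fulvestrant and frailty are not controlled, and show line where numbers allow.

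The cost is one SAP line, extra table columns and smaller cells. Starting dose, partner and line are already collected (SAP 5.5, Appendix 1), so no new data are needed. Cells will be too small in some countries. With 60 patients in the Netherlands, 60% on AI and 10% of those not at 125 mg (both assumed), the cell is 60 × 0.6 × 0.1 = 3.6 patients. Across wave 2 the same assumptions give 2060 × 0.6 × 0.1 = about 124 AI patients. With 20% of fulvestrant patients not at 125 mg, there would be 2060 × 0.4 × 0.2 = about 165. Pooling countries within indication is therefore a workable answer, and the existing sample-size condition covers the rest.
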